### 7.1.3.2 Total WOMAC Score Analysis (90 Days)

Page 13 of 27

Page 14 of 27

[figure not shown]
ANOVA on the change in Total WOMAC score between baseline and 180 days with treatment as a fixed effect and study site as the block effect will be used to compare the efficacy between Active and Control groups at 2-sided, level of significance.

In the case of data not being normally distributed, nonparametric tests, such as Wilcoxon Rank Sum test, will be utilized to assess the treatment efficacy.

[figure not shown]
#### 7.1.5 Exploratory Analyses

[figure not shown]
Page 15 of 27

Page 16 of 27

[figure not shown]
Page 17 of 27

Page 18 of 27

Page 19 of 27

Page 20 of 27

#### 7.1.6 Adjustments for Covariates

Not applicable.

#### 7.1.7 Disposition of Subjects

The number and percentage of subjects enrolled, randomized, treated, early termination in the study will be presented. Reasons for any screen failures and/or early terminations, including the relationship to COVID-19 related study disruption, will be summarized. In addition, the number and percentage of subjects who deviated from the study, including the relationship to COVID-19 related study disruption, will also be summarized.

#### 7.1.8 Description of Demographics and Baseline Characteristics

Demographic data, baseline characteristics, medical history, and concomitant medications will be summarized by means of descriptive statistics (number, mean, SD, median, minimum, and maximum) or frequency tables and analyzed using t-tests, chi-square tests, or Fisher's exact tests, as applicable. A listing of subjects affected by the COVID-19 related study disruption will be presented.

#### 7.1.9 Study Site Assessment

In addition to adjusting for study site in the primary efficacy analysis, in order to evaluate the consistency of efficacy across sites, subgroup analysis by study site will also be conducted. Study sites with less than 10 subjects will be analyzed using pooling techniques to provide more reliable inferences across sites.

#### 7.1.10 Subgroup Analyses

Exploratory analysis on efficacy parameters will be conducted on gender, age, BMI, and smoking status.

#### 7.1.11 Planned Interim Analyses

Page 21 of 27

#### 7.1.12 Multiple Comparisons / Multiplicity

There will be one interim analysis conducted when the study population reaches 50% of the total expected and a second interim analysis conducted after all subjects have completed the 180-day visit. Type I error will be adjusted for the interim analyses as mentioned in Section 7.1.11. Furthermore, one final analysis will be conducted upon study completion, which should mitigate any concerns of multiplicity.

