#### 3.1 Secondary Efficacy Endpoints

The secondary efficacy endpoints are as follows:

- Change in VAS score for pain between baseline and 180 days
- Change in Total WOMAC score between baseline and 180 days

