#### 7 STATISTICAL METHODS

#### 7.1 Statistical and Analytical Plans

#### 7.1.1 General Considerations

For the purposes of this protocol, osteoarthritis of the knee outcomes will be examined. The hypothesis to be tested is to confirm that the use of micronized dHACM offers a

Page 11 of 27

[figure not shown]
statistically significant advantage over 0.9% normal saline solution placebo for the treatment of osteoarthritis of the knee.

All statistical tests will be two-sided and will be performed at the significance, unless otherwise stated. Note that a penalty will be applied due to performing 2 planned interim analyses (see Section 7.1.11 for more details). Continuous data will be summarized by randomized Active and Control groups using descriptive statistics (number, mean, median, standard deviation [SD], minimum, and maximum). Categorical data will be summarized by randomized Active and Control groups using frequency tables (frequencies and percentages).

In addition to the efficacy analyses at the time point specified in the primary, secondary, and exploratory efficacy analyses, all efficacy parameters collected at various time points during the study will also be presented.

All analyses and summaries will be generated using SAS (SAS Institute, Inc., Cary, North Carolina).

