#### 7.1.3 Co-Primary Efficacy Analysis

This study consists of co-primary efficacy endpoints, which requires both endpoints to demonstrate success at 2-sided, level of significance.

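### The SAP's multiplicity section adjusts only for the interim looks; its appeal to one final analysis does not control error across the two Day-180 secondary endpoints

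*SAP*

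**What the plan says.** SAP 7.1.12 is the section on multiple comparisons. It describes two interim analyses and states "Type I error will be adjusted for the interim analyses as mentioned in Section 7.1.11". It closes by saying that a single final analysis at study completion should deal with multiplicity. Endpoints are not mentioned.

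SAP 7.1.3 sets the rule for the Day-90 pair: "This study consists of co-primary efficacy endpoints, which requires both endpoints to demonstrate success at 2-sided, level of significance" (the level itself is blanked). SAP 3.1 lists two secondary endpoints, change to Day 180 in VAS pain and in Total WOMAC.

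The readable paragraph on Day-180 Total WOMAC, printed after page 14, specifies "ANOVA on the change in Total WOMAC score between baseline and 180 days" with treatment and site in the model and a two-sided comparison. It states no condition on the co-primaries and no order relative to VAS. The protocol synopsis (Statistical Methods) gives primaries and secondaries the same ANOVA, also without a condition or order.

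SAP 7.1.1 applies a penalty for the interim looks and refers to 7.1.11 for its size. The body of 7.1.11 is not readable in the public copy.

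**The concern.** Repeated looks and multiple endpoints are two separate sources of error. Section 7.1.12 deals with the first and offers an argument about the number of analyses for the second. However few times the data are analysed, two endpoints tested at one analysis give two chances of a false finding. The co-primary rule does not help, because it covers only the Day-90 pair.

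The SAP's introduction says Phase 3 will be planned from the primary and secondary results at Day 90 and Day 180. Without a stated rule, one scale reaching significance at Day 180 after the Day-90 co-primaries have failed could be read as a finding. It could then steer the Phase 3 choice of endpoint and time point.

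**Working it through.** **Plan's own figure.** There is none to reproduce. The significance level is blanked and no family-wise error rate can be read. The sample size of about 466 does not enter, because the probabilities below are under the null.

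**Inputs**
- Two secondary endpoints (SAP 3.1), tested two-sided (SAP 7.1.1).
- Level per test: assumed 0.05, with 0.04 to show a penalised level. Critical values c = 1.960 and 2.054.
- Correlation r between the two test statistics: assumed 0.5 to 0.8.
- No gate or order: assumed, since the sections that might hold one cannot be read.
- Interim looks are not modelled.

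**Step 1: at least one false secondary, either direction.** P = 1 − P(|Z1| ≤ c and |Z2| ≤ c), with Z1, Z2 bivariate normal. With independent endpoints this is 1 − 0.95² = 0.0975 at 0.05, and 1 − 0.96² = 0.0784 at 0.04.

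| r | level 0.05 | level 0.04 |
|---|---|---|
| 0.5 | 0.0907 | 0.0732 |
| 0.7 | 0.0835 | 0.0674 |
| 0.8 | 0.0781 | 0.0631 |

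An interim penalty of this size lowers the inflation but does not remove it.

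**Step 2: favourable direction only, level 0.05.** P = 0.025 + 0.025 − P(Z1 > c and Z2 > c).
- r = 0.5: 0.0500 − 0.0046 = 0.0454
- r = 0.8: 0.0500 − 0.0110 = 0.0390

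The reference for a single test is 0.025.

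**Step 3: what a gate would change.** Four endpoints (two scales at two times) were simulated under the global null, with 2 million draws and level 0.05. Scale and time correlations were each 0.5 to 0.7, and the cross-correlation was their product.
- At least one favourable secondary while the co-primaries fail: 4.4% (both correlations 0.5) to 3.7% (both 0.7).
- At least one favourable secondary with both co-primaries also favourable, which is all a gate would let through: 0.15% to 0.42%.

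Of all false favourable secondaries, the share arising in trials with failed co-primaries is therefore 4.4 / (4.4 + 0.15) ≈ 97% to 3.7 / (3.7 + 0.42) ≈ 90%. A gate removes that part. When the gate is passed, the fixed order controls error between the two secondaries.

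**The case against.** The strongest reply is that the rule may exist where the public copy cannot be read. Section 5 on success criteria, Section 7.1.11 and the opening of the secondary analysis section are not visible, nor is any SAP text on the Day-180 VAS analysis. The layout supports this reply. The co-primary rule sits in the opening of 7.1.3; the Day-90 VAS paragraph does not repeat it and 7.1.12 does not cite it. The silence of the Day-180 WOMAC paragraph is therefore weak evidence that nothing governs the secondaries.

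This part stands, and it rules out two stronger readings:
- A reader might infer that the secondaries are tested at full level whether or not the co-primaries succeed. The documents do not establish either half: the level is blanked, an interim penalty applies, and a gate cannot be excluded.
- A reader might take the general statement in 7.1.1 to mean that exploratory comparisons are tested at the same level. That statement allows exceptions, and the body of 7.1.5 is not visible.

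It is also fair that nothing readable lets a lone secondary declare the study a success; the visible success rule in 7.1.3 requires both co-primaries.

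The reply does not rescue 7.1.12. That section reads as complete, in three continuous sentences. It points to 7.1.11 for the interim adjustment, points nowhere for endpoint multiplicity, and gives a reason that does not address it. Whether or not a gate exists elsewhere, the closing sentence is wrong as a statement about multiplicity.

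**Conclusion.** The point holds as a gap in 7.1.12: error is adjusted for the looks only, and the reason given for going no further does not cover two secondary endpoints. Whether the plan lacks a gate altogether cannot be settled from the public text.

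The size is conditional on there being no gate. Under the assumed levels and correlations, the chance of at least one false secondary finding is about 6% to 9%. At 0.05 it is 3.9% to 4.5% in the favourable direction, against 2.5% for one test. Nearly all of those false favourable results would come from trials whose co-primaries failed.

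Because this is a Phase 2B trial, the harm is over-reading a Day-180 result in Phase 3 planning, not a wrong confirmatory claim. It should be corrected, and the correction is cheap.

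**What to change.** If an equivalent rule already stands elsewhere in the SAP, cite it in 7.1.12 and delete the closing sentence. If not, replace that sentence with a fixed sequence:

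1. Name the analysis at which the co-primary decision is made. With two interim analyses and a final one, the gate is undefined until this is stated.
2. Test the secondaries only if both co-primaries succeed at their adjusted level at that analysis.
3. Then test Day-180 VAS pain, followed by Day-180 Total WOMAC, each at that same level, stopping at the first non-significant result.
4. If the gate is not passed or the sequence has stopped, report the remaining secondary p-values as nominal, with estimates and confidence intervals.

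The cost is one paragraph of SAP text, with no new data, subjects or procedures. The one small downside is that a lone positive secondary can no longer be called significant when an earlier test in the sequence fails.

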
Name of Investigational Product: Allogeneic Micronized Dehydrated Human Amnion/Chorion Membrane (Micronized dHACM), a.k.a. AmnioFix Injectable
 
Study Design: A Phase 2B, Prospective, Double-Blinded, Randomized Controlled Trial of the Micronized dHACM Injection as Compared to Saline Placebo Injection in the Treatment of Osteoarthritis of the Knee
 
Indication: Knee osteoarthritis (OA)
 
Objective: To determine the safety and effectiveness of micronized dHACM as compared to the 0.9% Sodium Chloride Injection, USP placebo control for the treatment of knee osteoarthritis
 
Sample Size: Approximately 466 subjects will be enrolled in this study. Subjects to be randomized 1:1 in treatment arms.
 
Study Plan: The estimated enrollment period is 26 months. Each subject will receive 1 injection and be evaluated for efficacy and safety during a 12-month observation period. A second injection (open-label access to micronized dHACM) will be offered to all subjects at the 180-day, 270-day, and 365-day time points, see open-label access section below; it may only be used once. The study is expected to be completed within 44 months, inclusive of enrollment and follow-up for all subjects.
 
Procedures and Assessments:
 
 • Treatment (approx. 1 day): Screening, pre-procedure evaluation, injection procedure, baseline evaluation. • Clinical Follow-up (365-545 days): Routine follow-up with physical examination; pain, function, and quality of life measurements: Visual Analog Scale (VAS) for Pain, VAS for Satisfaction, Western Ontario and McMaster Universities (WOMAC) osteoarthritis index, and Knee injury and Osteoarthritis Outcome Score (KOOS) will be evaluated at baseline, 30 days, 60 days, 90 days, 180 days, 270 days and 365 days after the initial treatment, and at time of open-label access and 30 days, 60 days, 90 days, and 180 days following the second injection should the subject elect to receive the open-label access treatment. Subject pain diaries will be completed at predefined intervals. • Safety Follow-up (365-545 days): Adverse Events (AEs), Serious Adverse Events (SAEs), and Unanticipated Adverse Events will be evaluated at 30 days, 60 days, 90 days, 180 days, 270 days and 365 days after the initial treatment, and at time of open-label access and 30 days, 60 days, 90 days, and 180 days following the second injection should the subject elect to receive the open-label access treatment. 
Primary Efficacy Endpoints (VAS for Pain and Total WOMAC): The co-primary efficacy endpoints are:
 
 • The change in VAS score for pain between baseline and Day 90 • The change in WOMAC osteoarthritis index total score (Total WOMAC score) between baseline and Day 90 
Primary Safety Endpoint: The primary safety endpoint is the proportion of product-related Adverse Events (AEs), Serious Adverse Events (SAEs), and unanticipated adverse events throughout the study.
 
Secondary Endpoints: The secondary efficacy endpoints for this study are:
 
 • Change in VAS score for pain between baseline and 180 days • Change in Total WOMAC score between baseline and 180 days

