#### **TABLE OF TABLES**

#### **TABLE OF FIGURES**

This Statistical Analysis Plan (SAP) is intended to act as an outline for the statistical interpretation of the data resulting from the Phase 2B Investigational New Drug (IND) trial, titled: "A Phase 2B, Prospective, Double-Blinded, Randomized Controlled Trial of the Micronized dHACM Injection as Compared to Saline Placebo Injection in the Treatment of Osteoarthritis of the Knee." Specific questions regarding this trial's design and/or implementation may be addressed by the study protocol (AIOA001 Protocol V2).

This study consists of two phases – Main Phase and Open-Label Extension Phase (Extension Phase). The Main Phase of the study includes subjects during the observation period where they received the randomized treatment only. The Extension Phase of the study includes the subjects who elected to receive an open-label injection of micronized dHACM injection at either of the 180-day, 270-day or 365-day visits, during the 180-day period following the open-label injection.

In order to facilitate the planning of a Phase 3 pivotal study based on results of the primary and secondary efficacy parameters at 90-day and 180-day, the randomized treatment for the Main Phase will be unblinded and a snapshot of the database will be taken after all randomized subjects completed the 180-day assessment. Formal database preparation process will be performed to ensure the integrity and quality of the database and an interim analysis of the primary and secondary efficacy endpoints as well as the exploratory efficacy endpoints up to the 180-day time point will be performed. At the end of the study, the database will be locked. The database lock process will be performed to ensure the integrity and quality of the database; and formal analyses will be performed.

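### The second interim analysis already holds every Day-90 and Day-180 visit: lock those data before unblinding, allow one full-data claim, and delete the clause that a later final analysis mitigates multiplicity

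*SAP*

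**What the plan says.** SAP 7.1.12 sets out three analyses: a look at half the planned population, "a second interim analysis conducted after all subjects have completed the 180-day visit", and a final analysis. Of the last it says that "one final analysis will be conducted upon study completion, which should mitigate any concerns of multiplicity". It also says that "Type I error will be adjusted for the interim analyses as mentioned in Section 7.1.11", and SAP 7.1.1 confirms that "a penalty will be applied due to performing 2 planned interim analyses".

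The SAP introduction describes the 180-day step. Main Phase treatment is unblinded, a database snapshot is taken, and the plan is to run "an interim analysis of the primary and secondary efficacy endpoints as well as the exploratory efficacy endpoints up to the 180-day time point". The stated purpose is to help plan a Phase 3 study. The snapshot is prepared with care: "Formal database preparation process will be performed to ensure the integrity and quality of the database". The lock comes only at the end of the study: "The database lock process will be performed to ensure the integrity and quality of the database; and formal analyses will be performed".

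The co-primary endpoints are changes to Day 90 (SAP 2.1) and the secondary endpoints are changes to Day 180 (SAP 3.1). SAP Section 4 makes every efficacy endpoint after Day 180 exploratory. The Protocol synopsis gives follow-up of 365 to 545 days, and its Statistical Methods text says that efficacy and safety data are submitted once follow-up is complete.

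**The concern.** For the endpoints that carry the efficacy claim, the second interim analysis is the full-data analysis. Three things follow.

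- It is counted as an interim look that incurs a penalty, although for these endpoints the study-end analysis brings no new visits. If Section 7.1.11 sets boundaries for three distinct looks, part of the alpha buys nothing.
- If the study-end analysis is the formal one, the decisive test is run after unblinding on Day-90/180 data that are not yet locked. Corrections made in that interval would be made with the allocation and the 180-day results available.
- The 7.1.12 clause credits the final analysis with a property that it does not have. A reader could take it as a reason why nothing further is needed.

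At stake are some power, and the credibility of a claim if the two analyses of the same endpoints were to differ.

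**Working it through.** The plan's significance level, power and interim boundaries are not visible, so there is no figure of its own to reproduce. The calculations below are illustrations.

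**Step 1: information at each analysis.** For the Day-90 and Day-180 endpoints the information fractions are about 0.5 at the first look, 1.0 at the second and 1.0 at study end. The last two are equal because Section 4 leaves only exploratory efficacy endpoints after Day 180.

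**Step 2: time between snapshot and lock.** The longest follow-up is 545 days, so the last visit can fall up to 545 − 180 = 365 days after the last 180-day visit.

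**Step 3: power recovered by charging two looks instead of three.** Assumptions: two-sided 0.05, 80% power in a fixed design, efficacy tested at 50% information, one endpoint, data unchanged after the 180-day look.

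- The full-data statistic Z2 has mean 1.960 + 0.842 = 2.802.
- The first-look statistic Z1 has mean 2.802 × √0.5 = 1.981. Its correlation with Z2 is √0.5 = 0.707.
- Power = 1 − P(|Z1| < c1 and |Z2| < c2). Setting both means to zero gives the type I error.
- Three-look critical values are the standard ones for equally spaced looks. Since the full-data result is tested twice, the more lenient of its two values applies.

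| Method | Two looks c1 / c2 | Type I error | Power | Three looks c1 / c2 | Type I error | Power | Recovered |
|---|---|---|---|---|---|---|---|
| O'Brien-Fleming | 2.797 / 1.977 | 0.0500 | 79.7% | 3.471 / 2.004 | 0.0452 | 78.8% | about 1 point |
| Pocock | 2.178 / 2.178 | 0.0500 | 75.6% | 2.289 / 2.289 | 0.0380 | 71.9% | about 4 points |
| Equal split | 2.241 / 2.241 | 0.0428 | 73.5% | 2.394 / 2.394 | 0.0290 | 68.2% | about 5 points |
| Haybittle-Peto | 3.291 / 1.960 | 0.0502 | 80.0% | same | same | same | nil |

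Information-based spending also recovers nothing, because it would register information of 0.5, 1 and 1 and spend no alpha on the repeat.

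The 50% look may mean 50% enrolled. With even accrual over 26 months, about 53 of the first 233 subjects would not yet have reached Day 90, so information is (233 − 53)/466 = 0.39. The gains are then 79.9 − 78.8 = 1.1 points (O'Brien-Fleming), 74.8 − 71.6 = 3.2 (Pocock) and 73.3 − 67.8 = 5.5 (equal split).

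**Step 4: retesting data changed after unblinding.** Suppose the two-look O'Brien-Fleming final test (1.977) is applied at the snapshot and again at study end, and either may claim success. Let Z3 = ρ·Z2 + √(1 − ρ²)·e, with e an independent standard normal variable. The values of ρ are illustrative; 20,000,000 null trials were simulated for one endpoint.

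| ρ | 1 (unchanged) | 0.999 | 0.995 | 0.99 | 0.98 |
|---|---|---|---|---|---|
| Type I error | 0.050 | 0.052 | 0.055 | 0.056 | 0.059 |

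Both co-primaries must succeed (SAP 7.1.3), so these are upper limits, reached only when the other endpoint is sure to succeed. With both nulls true and an assumed correlation of 0.7 between endpoints, the rate is about 0.017 to 0.020 for ρ from 0.999 to 0.98. With a three-look O'Brien-Fleming boundary the one-endpoint rate is 0.045 at each ρ.

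In no case does the extra analysis lower the error. Its effect is zero or a small increase.

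**The case against.** The case for the plan has real weight.

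- **The adjustment is stated.** A reader might infer that type I error is uncontrolled. The documents do not support that. 7.1.12 refers to an adjustment in Section 7.1.11 and presents the final analysis as an addition to it. The text of Sections 5 and 7.1.11 is not visible in the public copy, which is no fault of the plan, and may already name the decisive analysis.
- **The decisive analysis can be guessed.** The Phase 3 planning purpose of the snapshot, the placing of formal analyses at the lock, and submission after follow-up all suggest that the study-end analysis counts. If only that analysis may claim, the multiplicity between it and the 180-day analysis is answered. This stands in part. What answers it is a rule that only one analysis may claim, not the running of a further one, and the clause does not state such a rule. This reading also puts the decisive test after unblinding and before the lock.
- **Interim is a fair label for the trial as a whole.** Day 270/365 visits, the extension phase and safety are still outstanding. That stands; the point is limited to the co-primary and secondary endpoints.
- **Data changes may be small.** Formal preparation is planned for the snapshot, and no passage says that Day-90/180 data will be revised. That the study-end analysis repeats these tests is itself inferred, since its endpoints are not listed in the visible text.

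A reader might also infer a much larger power loss by supposing that success could be claimed only at a strict middle boundary for the 180-day look. Nothing in the documents suggests such a rule.

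**Conclusion.** The point holds as a minor to moderate one. On visible text alone, the 180-day analysis is complete for the co-primary and secondary endpoints yet is charged as interim, the lock follows unblinding, and the mitigation clause is wrong as a statement about error rates. Whether any alpha is wasted depends on the unseen Section 7.1.11: the cost runs from nothing to about 5 points of power for one endpoint. Any inflation needs two conditions together, namely data that change after the snapshot and permission to claim at either analysis. Even then it is slight. Neither condition is shown, so the finding is a gap in safeguards and not a demonstrated loss of control. All figures rest on an assumed level, power, boundary family and, for retesting, assumed correlations.

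**What to change.** 1. In SAP 7.1.12, delete the clause that the final analysis should mitigate multiplicity.
2. Clean and lock the Day-90/180 data before the 180-day unblinding. Allow only one full-data claim on the co-primary and secondary endpoints, made from those locked data. If Section 5 or 7.1.11 already names the decisive analysis, keep that choice.
3. If Section 7.1.11 sets three distinct looks for these endpoints, share alpha only between the 50% look and the single full-data analysis, using the Day-90 information actually available at the first look. As an example at an assumed 0.05, two-look O'Brien-Fleming levels are 0.0052 then 0.0480 at 50% information, or 0.0016 then 0.0493 at 39%.
4. Keep the study-completion analysis for the primary safety endpoint and its between-group comparison, the Day 270/365 results and the extension phase. Report later corrections to Day-90/180 data as sensitivity analyses.

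The cost is SAP wording and possibly a revised boundary table. Formal database preparation is already planned for the snapshot, so locking these data then should add little work. The small downside is that later corrections would not change the formal verdict.
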